## Non-interventional study protocol

### Strontium ranelate (ATC M05BX03)

Title	European Program of Post-Authorization Safety Studies for Protelos®/Osseor® through EU-ADR Alliance
Protocol identifier	version 3.0
Date of last version of protocol	7 January 2015
EU PAS register number	Study not registered yet
Active substance	Strontium ranelate (ATC M05BX03)
Medicinal product	Protelos®/Osseor®
Product reference	EU/1/04/288/001-006 (Protelos®) EU/1/04/287/001-006 (Osseor®)
Procedure number	EMA/H/C/000560/ANX 034 EMA/H/C/000561/ANX 034
Marketing authorization holder(s)	Les Laboratoires Servier
Joint PASS	No
Research question and objectives	The aims of this PASS program are: 

1. To study the effectiveness of the newly established risk minimization measures by characterizing utilization patterns of SR and estimating the prevalence of contraindications and restrictions of indication amongst incident and prevalent SR users

2. To estimate and compare the incidence rates of cardiac and thromboembolic events in new users of SR and new users of bisphosphonates

**Country(-ies) of study** Denmark, Italy, Netherlands, Spain, and United Kingdom.

**Authors** [name], MD MSc PhD  
[name]. [name] [name], PhD

## 2. LIST OF ABBREVIATIONS

ATC	Anatomical Therapeutic Chemical
AUH	Aarhus University Hospital, Department of Clinical Epidemiology regional database
BP	Bisphosphonates
CHMP	The Committee for Medicinal Products for Human Use
CPRD	Clinical Practice Research Datalink
CVD	Cerebrovascular Disease
DHPC	Direct Healthcare Professional Communication
EC	European Commission
ENCePP	European Network of Centres for Pharmacoepidemiology and Pharmacovigilance
EMA	European Medicines Agency
EU	European Union
GPP	Good Pharmacoepidemiology Practices
HSD	Health Search CSD Longitudinal Patient Database
ICD	The International Classification of Diseases
IHD	Ischemic Heart Disease
IPCI	Integrated Primary Care Information Project
ISPE	International Society for Pharmacoepidemiology
MAH	Marketing Authorization Holder
PAD	Peripheral Arterial Disease
PASS	Post-Authorization Safety Study
PRAC	Pharmacovigilance Risk Assessment Committee
PSUR	Periodic Safety Update Report
REB	Research Ethics Board
RMM	Risk Minimization Measures
RRE	Remote Research Environment
SIDIAP	Sistema de Información para el Desarrollo de la Investigación en Atención Primaria
SPC	Summary of Product Characteristics
SR	Strontium Ranelate
STROBE	Strengthening the Reporting of Observational Studies in Epidemiology
TIA	Transient Ischemic Attack
THIN	The Health Improvement Network
UMLS	Unified Medical Language System
WHO	World Health Organization

#### 4. ABSTRACT

Title	
European Program of Post-Authorization Safety Studies for Protelos®/Osseor® through EU-ADR Alliance
 
Study number: CLE-12911-046
 
Protocol version 3.0
 
Authors: [name], [name]
 
Date: 07 January 2015

Rationale and background	
Strontium ranelate (Protelos®/ Osseor®) has been authorized since 2004 in the European Union for the treatment of osteoporosis in postmenopausal women to reduce the risk of vertebral and hip fracture. Since June 2012, strontium ranelate is also approved for the treatment of osteoporosis in adult men at increased risk of fracture.
 
In the frame of 13th PSUR assessment, data submitted raised concern regarding cardiovascular safety beyond the already recognized risk for venous thromboembolism. As a result of this assessment, an increased risk for serious cardiac disorders, including myocardial infarction has been identified and risk minimization measures specifically targeting this identified risk were recommended by the CHMP. These risk minimization measures included a restriction of the target population by excluding patients with established, current or past history of ischaemic heart disease, peripheral arterial disease and/or cerebrovascular disease and/or uncontrolled hypertension, and restricting the indication to severe osteoporosis in postmenopausal women at high risk for fracture to reduce the risk of vertebral and hip fractures and the treatment of severe osteoporosis in adult men at increased risk of fracture. In addition, strontium ranelate therapy should only be initiated by a physician with experience in the treatment of osteoporosis. These changes were disseminated in the form of a DHPC in May 2013.
 
In view of this newly identified risk of serious cardiac disorders, an overall benefit/risk review under Article 20 of regulation (EC) No 726/2004 started in May 2013 and was finalized on 20 February 2014. This led to a restriction of the indication to patients (postmenopausal women and men) with severe osteoporosis at high risk of fracture for whom treatment with other medicinal products approved for

	
the treatment of osteoporosis is not possible due to, for example, contraindications or intolerance. As part of RMM, a new DHPC was disseminated in March 2014.
 
The overarching aims of the proposed study are:
 

1. To study the effect of the risk minimization measures for Strontium Ranelate

2. To estimate and compare the incidence rates of cardiac and thromboembolic events in new users of SR and new users of bisphosphonates

Research objectives	
question and PRIMARY OBJECTIVES:
 
Effectiveness of risk minimization
 

1. To characterize utilization patterns of strontium ranelate in three periods: up to May 2013 (first DHPC), between June 2013 and March/2014 (second DHPC), and from April 2014 onwards.

2. To estimate the prevalence of contraindications in SR users during the same three periods.

3. To calculate the prevalence of SR users who fulfil the new indications (after imposition of new restrictions of use) for SR therapy in the same three periods.

 
Safety
 

1. To estimate the incidence rates of cardiac and thromboembolic events in SR users with and without contra-indications prior and after June 2013.

2. To compare the risk of cardiac and thromboembolic events between new users of SR and new users of oral bisphosphonates without contra-indications, both before and after June 2013.

Study design	
Multi-national multi-database approach with:
 

1. Population-based cohort study

2. Nested case control analysis in a cohort of new users of strontium ranelate or oral bisphosphonates (BP).

Population	
Setting
 
The study will be conducted using routinely collected health care data from databases that participate in the EU-ADR Alliance. EU-ADR Alliance is a network of research institutes that conduct

pharmacoepidemiological research. For this study data will be used from 5 EU countries: Denmark, Italy, the Netherlands, Spain, and the United Kingdom.

### **Study population**

The study population will comprise the entire source population for the measurement of risk minimization effectiveness. It comprises a cohort of new SR and oral bisphosphonate users for the comparative safety study. Specific inclusion and exclusion criteria will apply

Study period: the study period will start in 2004 (2006 for SIDIAP) and end at latest data supply. This period will be split in three analysis periods for the analysis of effectiveness of RMM:

1. Up to May 2013 (first DHPC and SmPC revision): *reference period*
2. From June 2013 to March 2014 (second DHPC and SmPC revision): *transitional period*
3. And from April 2014 onwards: *assessment period*

Similarly, the study period will be split in two analysis periods for the safety studies:

1. Up to May 2013
2. From June 2013 onwards

## **Variables**

### **Safety endpoints**

1. Acute myocardial infarction
2. Thromboembolic events (deep venous thrombosis and pulmonary embolism)
3. Cardiovascular death

### **Contra-indications**

Venous thromboembolism, ischaemic heart disease, peripheral arterial disease and/or cerebrovascular disease, uncontrolled hypertension

### **New indications/prescribing conditions**

Experienced prescriber; treatment not in first line; severe osteoporosis

## **Data sources**

Data from 5 electronic healthcare databases (all listed in ENCePP registry of data sources except Aarhus)

1. The Integrated Primary Care Information Project (IPCI) from the Netherlands,
2. The Sistema d'Informació per al Desenvolupament

	
de la Investigació en Atenció Primària (SIDIAP) from Spain,
 

3. The Health Improvement Network (THIN) from the UK,

4. Aarhus Database (Denmark), and

5. The HSD-Thales database (Italy)

Study size	
All users of strontium ranelate during study period (> 100,000 prevalent and 30,000 incident users expected based on feasibility) & cohort of new oral bisphosphonates users for comparison of safety.

Data analysis	
Utilization of strontium ranelate
 
Population level: Incidence and prevalence of SR use will be described by year, month, age and gender.
 
Patient level: patterns of use (switching, stopping and duration) will be described for all incident and prevalent users. Baseline characteristics will be described for all incident and prevalent SR users. Analyses will be stratified by period (as described above), by month, country, age, and gender.
 
Prevalence of contra-indications and new indications of use/restrictions
 
We will assess the prevalence (and 95% Confidence Intervals) of contra-indications and new indications/restrictions for incident and prevalent users of SR at a patient level in the three periods defined above (reference, transitional, and assessment), as well as by year, month, country, age and gender.
 
Interrupted time series analyses will be carried out to assess the impact of the RMM on these. Each contributing data source will be analysed using an interrupted times series design (Ramsay, 2003), using repeated measures before (up until May 2013) and after intervention (from April 2014 onwards) to control for secular trends. Trends in the reference period (up until May/13) will therefore be compared to those in the assessment period (April/14 onwards) using the transitional period (June/13 to March/14) as a lag time for the intervention to take effect. Sensitivity analyses excluding participating countries where legal restrictions have been put in place for the prescription of SR in primary care (i.e. Spain) will be carried out and reported accordingly.
 
Safety

Crude, as well as age and sex-specific incidence rates of cardiac, thromboembolic (deep vein thrombosis and pulmonary embolism) events, and cardiovascular death during use of SR will be estimated in strata of persons with 0, 1, 2, or more contra-indications amongst persons initiating SR prior and after June 2013. Estimates will be further stratified by age and gender.

The risk of cardiac, thromboembolic events and cardiovascular death will be compared between current use of SR and past use of SR/BP as well as between current use of SR and current use of BP, in persons without contra-indications at start of osteoporosis therapy.

Each case will be matched by age, index date, gender, and country/data source to 10 controls.

Nested case-control analyses will be done using conditional logistic regression.

Sensitivity analyses excluding participating countries where legal restrictions are in place for the prescription of SR in primary care (i.e. Spain) will be reported.

Milestone	Planned date
Protocol submission to EMA	by 30 June 2014
Protocol approval by EMA	March 2015 *
Contract signature for study roll-out phase	April 2015*
Registration in the EU PAS register	April 2015*
Start of data collection	April 2015*
Statistical Analysis Plan	May 2015
End of data collection	End of June 2015
PSUR Update 1	October 2015
Start of data collection (second wave)	April 2016
End of data collection (second wave)	End of June 2016
PSUR Update 2	October 2016
Start of data collection (third wave)	April 2017
End of data collection (third wave)	End of June 2017
PSUR Update 3	October 2017
Final report of study results	End of November 2017

\*Delay will impact the subsequent dates.

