## Safety

1. To estimate the incidence rates of cardiac and thromboembolic events in SR users with and without contra-indications prior and from June 2013.
2. To compare the risk of cardiac and thromboembolic events between new users of SR and new users of oral bisphosphonates without contra-indications, both before and from June 2013.

All of these research objectives will be addressed for the overall eligible population but also after stratification by country, gender, period (three analysis periods (reference, transitional, and assessment) for the assessment of RMM effectiveness, and two periods (before and from June 2013) for the safety studies), month and age, and presence/absence of contra-indications, when applicable/relevant.

In addition, sensitivity analyses excluding participating countries where legal restrictions are in place for the prescription of SR in primary care (i.e. Spain) will be carried out for both the RMM effectiveness and safety studies, and reported accordingly.

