### 9.2.3. Study population

The study population for this study comprises:

1. The source population for the measurement of RMM effectiveness.
2. New (not using drug in year prior to cohort entry) strontium ranelate users and new oral bisphosphonates users (BP) for the safety study.

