#### Duration of treatment

In order to create episodes of drug use the duration of treatment will be calculated using the following definitions:

- *Legend duration*: Total units /prescribed daily dose.
- *Normal duration*: Total number of defined daily doses (DDD) prescribed: Total Units\*Strength)/DDD value.

In order to define periods of continuous use of study drugs, any two prescriptions of the same drug will be concatenated if the gap between the end of the first of the two prescriptions and the start of the second of the two prescriptions was less than 30 days apart, a carry-over period of 30 days will be added after last prescription to account for lack of compliance and carry-over effects.

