#### Exposure categorization for safety studies

For the incidence rate calculations the period of drug use will be divided in mutual exclusive periods of a month to be able to investigate the rate of cardiac events during current, recent or past use. The period 0-180 days after cessation of study drugs use will be classified as recent use and the period 181 days or more will be classified as past use. If patients switch from SR to BP or vice versa, they will contribute to the respective exposure category.

For the case control study we follow the same categorization. A patient will be classified as current user if the last prescription is ongoing or stopped less than 30 days ago before the index date. Patients will be classified as recent users if last prescription stopped between 30 and 180 days before the index date. Patients are past users if the last prescription for a study drug stopped more than 180 days before index date.

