### 9.7.3.3. Relative risks

Using a matched case control approach we will use conditional logistic regression to estimate the association with the occurrence of endpoints and between current use of SR and 1) past use of study drugs; 2) current use of bisphosphonates. Control for confounding will be based on the change in estimate method as proposed by Greenland *et al* (1993). All analyses will be stratified by period. We will primarily consider factors measured at baseline, and only for those at index date for which we are sure they cannot be an intermediate between drug exposure and outcome.

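### Both safety reference groups can contain former strontium ranelate users, and a recent switcher to a bisphosphonate counts as current on both drugs; if SR risk outlasts the exposure windows, the odds ratio can be pulled toward 1

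*Protocol*

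**What the plan says.** Safety objective 2 in Protocol Section 8 is "To compare the risk of cardiac and thromboembolic events between new users of SR and new users of oral bisphosphonates without contra-indications". The contrasts meant to answer it appear in the Abstract (Data analysis, Safety), "compared between current use of SR and past use of SR/BP as well as between current use of SR and current use of BP", and in Section 9.7.3.3, "between current use of SR and 1) past use of study drugs; 2) current use of bisphosphonates". Both places pool past SR with past BP.

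The exposure rules are in Section 9.3.3:

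- Switchers: "If patients switch from SR to BP or vice versa, they will contribute to the respective exposure category".
- Current use: a patient is "classified as current user if the last prescription is ongoing or stopped less than 30 days ago".
- Recent use: stopped 30 to 180 days before the index date.
- Past use: "Patients are past users if the last prescription for a study drug stopped more than 180 days before index date".
- Duration of treatment: "a carry-over period of 30 days will be added after last prescription to account for lack of compliance and carry-over effects".

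Section 9.2.3 defines the safety cohort as "New (not using drug in year prior to cohort entry) strontium ranelate users and new oral bisphosphonates users (BP) for the safety study". It does not say that a new user of one study drug must also be free of the other.

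**The concern.** Objective 2 needs a reference that represents bisphosphonate treatment. As the rules stand, a patient leaving SR can enter either reference group:

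- **Past use.** Someone more than 180 days off SR is pooled with someone more than 180 days off BP.
- **Current BP.** Someone who stops SR and starts BP is a current BP user from the first BP prescription. The recent-use category does not protect this reference, because the switcher never passes through it.

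There is also a gap in the rules. A patient on BP whose SR stopped 10 days ago has an ongoing BP prescription and an SR prescription that stopped less than 30 days ago, so is current on both. Nothing says which drug takes an event on that day.

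Any SR risk that continues after SR stops would be counted in the reference, and a real harm would look smaller. The missing precedence rule matters whatever the size of that effect, because the exposure categories are built locally in five databases.

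**Working it through.** **1. The plan's own figure.** Section 9.5.2 gives 415 MI cases for 90% power at odds ratio 1.5, alpha 0.05, 20% SR use among controls and 10 controls per case. Sidedness is not stated; two-sided is used here.

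- Exposure among cases: 0.2 × 1.5 / (1 + 0.2 × 0.5) = 0.2727.
- Unpooled two-proportion formula: (1.960 + 1.282)² × (0.2727 × 0.7273 + 0.2 × 0.8/10) / 0.0727² = 426 cases.
- Matched case-control formula (Dupont): 384 with no exposure correlation within sets, 420 with an assumed correlation of 0.2.
- Power of the two-proportion test (pooled variance under the null) at 415 cases: 0.92.

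The 415 is therefore reproduced closely enough to serve as a baseline. At the 570 cases that the same section expects, the baseline power is 0.975.

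**2. Dilution formula.** Let f be the share of former SR users in the reference and c the share of the SR excess risk that persists after stopping. Then

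observed OR = OR / (1 + f × c × (OR − 1)).

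With c = 0 the observed OR is 1.5 for every f.

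**3. Inputs that the protocol does not give.** Neither f nor c is stated. For past use, f is taken from the planned cohort as an assumption: 25,128 / (25,128 + 125,640) = 16.7%, or the 20% SR share that Section 9.5.2 uses for controls. For c, 0.5 and the extreme value 1 are shown.

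**4. Past-use contrast, true OR 1.5.**

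| f | c | Observed OR | Power, 415 cases | Power, 570 cases |
|---|---|---|---|---|
| any | 0 | 1.50 | 0.92 | 0.975 |
| 16.7% | 0.5 | 1.5/1.0417 = 1.44 | 0.86 | 0.94 |
| 20% | 0.5 | 1.5/1.05 = 1.43 | 0.84 | 0.93 |
| 16.7% | 1 | 1.5/1.0833 = 1.38 | 0.77 | 0.88 |
| 20% | 1 | 1.5/1.10 = 1.36 | 0.73 | 0.85 |

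These powers keep the plan's simplification that all cases and controls enter one exposed-versus-unexposed comparison. They show relative loss, not the power of the final model.

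**5. Current-BP contrast.** The same formula applies, but f depends on how many SR users move to BP, and the protocol gives no such rate. For scale only, f = 5% gives 1.5/1.0125 = 1.48 with half the excess persisting and 1.5/1.025 = 1.46 with all of it.

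**6. Do the planned safeguards cover this?**

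- Section 9.3.4 lists prior anti-osteoporosis drugs (ATC M05B) as a covariate. That class holds both SR (M05BX03) and the bisphosphonates (M05BA), and the look-back is one year.
- Section 9.9 keeps a covariate only on a 10% change in the estimate. With f = 20% and half the excess persisting, the shift from 1.50 to 1.43 is about 5%.
- Section 9.7.5 varies the gap and the risk window. That bears on carry-over length, but it neither separates drug histories nor settles which drug takes overlapping time.

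**The case against.** The strongest case against is that past use is a sound reference. Current versus past use contrasts time on drug with time off drug, and past users are more than 180 days off. Section 9.9 expects confounding by indication, with SR patients having more severe osteoporosis, and a reference that includes past SR users limits it. The only carry-over in the protocol is 30 days, and the carry-over and current-use windows agree with each other; only the precedence rule is missing. Contrast 2 in Section 9.7.3.3 already addresses objective 2, and Section 9.7 leaves detail to a statistical analysis plan that is not available here. Section 9.2.6.2 can also be read as requiring a year without either drug before entry.

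Most of this stands, and it limits the point. It does not remove it. The pooling and the switching rule are stated in the protocol, and a washout at entry does not stop a patient from switching afterwards.

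A reader might infer more in three ways:

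- **That SR is simply being compared with itself, or that the odds ratio is biased.** The documents do not support either. Dilution needs risk that outlasts the windows, and the protocol does not say that it does.
- **That many SR users will move into the references, because new use is expected to fall from 5,819 in 2012 to 500-1,000 a year.** That is a fall in new starts, not a count of people leaving SR. The Italian bar on renewal by GPs concerns one database.
- **That the past-use reference should be replaced by past BP users who never took SR.** That gives up protection against confounding by indication and should not be required.

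There is a further fair objection: cleaning only the BP side is one-sided. Section 9.5.1 cites 40.4% to 47.9% second-line use of SR, so many current SR users will have taken another osteoporosis drug before. The fix below allows for this.

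**Conclusion.** The concern holds in a limited form. By the stated rules, former SR users can be in both references, and a recent switcher is current on both drugs with no rule to decide between them.

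The effect on the result is conditional. It is zero if SR risk ends with the window. On the past-use contrast, a true 1.5 falls to about 1.44-1.43 with half the excess persisting and to 1.38-1.36 in the extreme. At the 570 cases the plan expects, power stays at 0.85 or above in all these scenarios; the lower values of 0.73-0.86 belong to the minimum count of 415. All of this rests on an assumed 16.7-20% share of former SR users and an assumed degree of persistence. The size for the current-BP contrast cannot be given. That contrast is the more exposed of the two, because switchers enter it with no SR-free interval.

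This is worth correcting because it is cheap and the planned safeguards do not supply it. It is not evidence that the planned estimates are wrong.

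**What to change.** In Sections 9.3.3 and 9.7.3.3:

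1. State that, for switchers, time within the 30-day SR carry-over is assigned to SR even if BP has started.
2. In the same conditional logistic model, use separate levels for current SR, current BP without prior SR, current BP after SR, past SR and past BP, with a rule for past users who took both.
3. For objective 2, report current SR against current BP without prior SR, and show current BP after SR alongside.
4. Keep the past-use reference, but also show past SR and past BP separately.
5. Report current SR with and without prior BP use, so that the restriction on drug history is not one-sided.

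The Abstract should be aligned with this wording. No new data are needed, since prescription histories are already extracted. The cost is slightly wider intervals, because each reference is smaller, and a few sparse exposure levels, most likely in the databases with few SR users and in the period from June 2013.
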